8.2 Inclusion Criteria – Cohort A

A subject must meet the following criteria to be eligible for entry into the study:

- 1) Age \geq 18 years old.
- 2) History of NSCLC with EGFR mutation (either exon 19 deletion or L858R mutation or an EGFR mutation that has had a clinical response to erlotinib, afatinib, or gefitinib in the patient being enrolled).
- 3) Occurrence or progression of BM while receiving first line therapy (either erlotinib or afatinib or gefitinib) for at least 14 days. Patients may have received osimertinib (or other agents inhibiting the T790M EGFR mutation) as second line therapy. If BM progression occurs after osimertinib, patient will be eligible.
- 4) At least 1 measurable BM by RECIST 1.1 criteria (\geq 10mm in longest diameter). Target lesions must not have received stereotactic radiotherapy (SRS). If subject had prior whole brain radiotherapy (WBRT), progression in any measurable BM lesion must have occurred at least 3 months after the end of WBRT. Subjects with asymptomatic brain metastases may be enrolled without prior radiation therapy to the brain. Subjects with minimally symptomatic brain metastases may be enrolled without prior radiation therapy to the brain if they do not require immediate surgical or radiation therapy in the opinion of the treating investigator and in the opinion of a radiation therapy or neurosurgical consultant.
- 5) Subjects in Cohort A may have asymptomatic LM detected by MRI. (Subjects with symptoms or signs attributed to LM will be enrolled in Cohort B whether or not they have brain metastases.)
- 6) No clinically significant progression outside of the CNS on most recent EGFR inhibitor therapy.
- 7) Eastern Cooperative Oncology Group (ECOG) Score \leq 2.
- 8) No history of another malignancy in the 5 years prior to study entry, except treated non-melanoma skin cancer or superficial bladder cancer or carcinoma-in-situ of the cervix or Stage 1 or 2 cancers of other sites that have been treated surgically and have not recurred.

-
- 9) Adequate organ and bone marrow functions as follows:
- a) Serum creatinine ≤ 1.5 mg/dL
 - b) Total bilirubin $\leq 1.5 \times$ the upper limit of normal (ULN; except in patients diagnosed with Gilbert's disease where bilirubin must be $\leq 3 \times$ ULN).
 - c) Alanine aminotransferase (ALT) and aspartate aminotransferase (AST) $\leq 3 \times$ ULN
 - d) WBC $> 3000/\text{mm}^3$
 - e) Absolute neutrophil count $\geq 1500/\text{mm}^3$

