8.4 Inclusion Criteria – Cohort B

A subject must meet the following criteria to be eligible for entry into the study:

1. Age \geq 18 years old.
2. History of NSCLC with EGFR mutation (either exon 19 deletion or L858R mutation or of an EGFR mutation that has had a clinical response to erlotinib, afatinib, or gefitinib in the patient being enrolled).
3. Presentation with LM at initial presentation with no prior systemic treatment, or occurrence or progression of LM while receiving first line therapy (either erlotinib or afatinib or gefitinib) for at least 14 days. Patients may have received osimertinib (or other agents inhibiting the T790M EGFR mutation) as second line therapy. If LM progression occurs after osimertinib, patient will be eligible.
4. Presence of at least one CTCAE 4.03 symptom or sign of at least Grade 1 attributed to leptomeningeal metastases.
5. Diagnosis of LM by:
 - a) Cytological evidence in CSF sample of LM due to NSCLC, and/or
 - b) Findings on gadolinium-enhanced MRI
6. No clinically significant progression outside of the CNS on most recent EGFR inhibitor therapy.
7. Concomitant brain metastases and brain metastases previously treated with radiation therapy are allowed. (Subjects with symptoms or signs attributed to LM will be enrolled in Cohort B whether or not they have brain metastases.)

-
8. ECOG Score ≤ 2 .
 9. No history of another malignancy in the 5 years prior to study entry, except treated non-melanoma skin cancer or superficial bladder cancer or carcinoma-in-situ of the cervix or Stage 1 or 2 cancers of other sites that have been treated surgically and have not recurred.
 10. Adequate organ and bone marrow functions as follows:
 - a) Serum creatinine ≤ 1.5 mg/dL
 - b) Total bilirubin $\leq 1.5 \times$ ULN (except in patients diagnosed with Gilbert's disease where bilirubin must be $\leq 3 \times$ ULN).
 - c) ALT and AST $\leq 3 \times$ ULN
 - d) WBC $> 3000/\text{mm}^3$
 - e) Absolute neutrophil count $\geq 1500/\text{mm}^3$
 - f) Platelet count $> 100,000/\text{mm}^3$
 - g) Hemoglobin > 8 g/dL
 11. Serum potassium and magnesium levels above the LLN.
 12. No coexisting medical problems of sufficient severity to limit compliance with the study.
 13. Willing and able to sign written informed consent and be able to comply with the study protocol for the duration of the study.

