14 EFFICACY

In addition to bone scan at screening, CT scans of the thorax and abdomen will be performed at screening, after Cycle 2, and then every two cycles thereafter until disease progression.

Radiological disease assessments by brain MRI will be performed at screening, at C2D1, at C3D1, and then every two cycles until disease progression. Response for peripheral disease and for BM will be evaluated according to RECIST, Version 1.1. Response will be recorded separately for non-CNS disease, for BM, and for LM. All CT and MRI scans will be collected for central review. All clinical decisions during the study will be based on local site radiology assessments, which will also be used for the primary efficacy analysis.

For subjects with BM (Cohort A and Cohort C) efficacy will be evaluated by RECIST 1.1 criteria separately for non-CNS tumor lesions and for BMs at Screening, at Cycle 2 Day 1 (for BM), at Cycle 3, and then every 2 cycles (approximately 8 weeks) thereafter until disease progression.

For subjects with LM (Cohort B), symptoms attributed to leptomeningeal disease will be evaluated at screening, Cycle 1 Day 1, at Cycle 1 Day 14, at Cycle 2 Day 1, at Cycle 3, and then every 2 cycles (approximately 8 weeks) thereafter until disease progression.

The response efficacy endpoints will be evaluated separately for peripheral disease, for BM, and for LM, and a summary response will also be derived (See Table 14-1). For LM, if positive CSF cytology and MRI diagnostic findings were both present at screening, complete response (CR) requires the absence of LM by both modalities. For LM, CR also requires the complete resolution of symptoms and signs attributed to LM. Best overall response, duration of response, and duration of stable disease will be reported, based on the examples in Table 14-1. The median PFS, rate of CNS non-progression at 3 and 6 months, non-CNS time to progression, CNS TTP, and median OS also will be assessed.

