Subjects with limited CNS or extra-CNS disease progression (oligoprogressive disease) may receive local ablative therapy (radiation therapy or surgery) and then be continued on tesevatinib. This practice is consistent with data indicating that some patients with NSCLC on TKI therapy who have oligoprogressive disease appear to have significant periods of additional disease control with this approach.¹⁹ Any such patients will be considered to have disease progression for analyses of PFS and for analyses of progression in the relevant (CNS or extra-CNS) compartment at the time of detection of oligoprogressive disease.

Subjects with scans that are on the “borderline” of disease progression (e.g. 21% increase in sum of target lesion diameters or equivocal findings on CSF cytology or MRI) but for whom the investigator determines a clinical benefit may occur in the study. These subjects will be allowed to continue in the study after discussion with the medical monitor. If improvement is documented at the next subsequent staging time point (e.g. 17% increase in sum of target lesion diameters or stable CNS symptoms), the subject will continue on study. If worsening is documented (e.g. 30% increase in sum of target lesion diameters or worsening of CNS symptoms), the subject should be discontinued from the study, and the progression date should be the original date on which “borderline” disease progression was first documented. If stable, then they will be followed until improvement or worsening occurs.

Table 14-1: Summary Response Examples

Peripheral Tumor ¹		Brain Metastases ¹		Leptomeningeal Metastases	Summary Response ³
Measurable	Non-measurable	Measurable	Non-Measurable		
CR	CR	CR ²	CR ²	CR ²	CR, peripheral, BM and LM
Non-CR, non-PD	Non-CR, non-PD	PR ²	None	Non-CR, non-PD	PR, BM only
Non-CR, non-PD	Non-CR, non-PD	CR ²	CR ²	Non-CR, non-PD	CR, BM only
Non-CR, non-PD	Non-CR, non-PD	Non-CR, non-PD	Non-CR, non-PD	CR ²	CR, LM only
Non-CR, non-PD	Non-CR, non-PD	Non-CR, non-PD	Non-CR, non-PD	None	CR, LM only
Non-CR, non-PD	Non-CR, non-PD	CR ²	None	CR ²	CR, BM and LM only
Non-CR, non-PD	Non-CR, non-PD	Non-CR, non-PD	Non-CR, non-PD	Non-CR, non-PD	SD

BM = bone metastases; CR = complete response; LM = leptomeningeal metastases; PD = progressive disease; PR = progressive response; SD = stable disease

- Using RECIST 1.1 criteria

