- Diagnosis of BM CR or PR, or LM CR, requires that steroids be at or lower than dose of steroids at Cycle 1 Day 1 (if subject is receiving steroids)
- All summary response examples assume that no new lesions are present. A new peripheral tumor or brain metastasis, or symptom progression of LM will lead to a summary response of PD in that category.

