14.2 Cohort B – Leptomeningeal Metastases

For subjects with LM, symptoms attributed to leptomeningeal metastases will be evaluated at screening, Cycle 1 Day 1, Cycle 1 Day 14, Cycle 2 Day 1, Cycle 3 Day 1, and then every 2 cycles (approximately 8 weeks) thereafter until disease progression, as well as at the End of Drug Treatment visit. CTCAE v4.03

(www.hrc.govt.nz/sites/default/files/CTCAE%20manual%20-%20DMCC.pdf) will be utilized for the evaluation of symptoms and signs attributed to leptomeningeal metastases. Symptom improvement is defined as a decrease in 1 grade in at least one CTCAE v4.03 symptom or sign attributed to leptomeningeal metastases without worsening of other neurologic symptoms or signs attributed to leptomeningeal metastases. Symptom progression is defined as an increase of 1 grade in at least one CTCAE v4.03 symptom attributed to leptomeningeal metastases or the appearance of new symptoms or signs of LM. Symptoms or signs attributed to leptomeningeal metastases will be followed as one component of the efficacy evaluation for Cohort B.

For subjects with LM, NSCLC cells in the CSF will be evaluated during the study (screening, Day 14 of Cycle 1, and on Day 1 of Cycle 3) for malignant cells both by standard cytological analysis and by a rare cell detection methodology. CSF obtained at the same time points will be evaluated for protein and glucose levels. Response will be based on standard cytological analysis if cytology was positive at screening. Response categories will be CR (no malignant cells, which must be present on 2 consecutive CSF evaluations to support response of CR), and non-PR, non-PD (continued presence of malignant cells). PD will not be defined by CSF cytology.

For subjects with LM (Cohort B), CSF for isolation of cell-free DNA will be collected at screening, Day 14 of Cycle 1, and Day 1 of Cycle 3. Evaluation for EGFR mutations will be performed. Quantitation of EGFR mutations in cell-free DNA will be utilized for an exploratory efficacy analysis.

LM will also be evaluated by serial MRI of the brain. For patients with positive findings of LM on MRI at screening, response categories will be CR (no evidence of LM on MRI), or non-PR, non-PD (continued presence of evidence of LM on MRI). PD for LM will not be defined by MRI.

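### Protocol Table 14-1, row 5, assigns an LM-only complete response to a subject whose LM entry is None and who has no response elsewhere; only descriptive outcomes are exposed

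*Protocol*

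**What the plan says.** Protocol section 14 has response assessed separately for peripheral disease, BM and LM, with a summary response derived by reference to Table 14-1. The table carries more than the summary: "Best overall response, duration of response, and duration of stable disease will be reported, based on the examples in Table 14-1". The synopsis says the same.

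Counting body rows from the top, row 5 has non-CR, non-PD in both peripheral cells and both BM cells. Its last two cells, LM and summary response, read "None CR, LM only".

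The rules for LM response stand in the text:

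- Section 14.2, MRI: "For patients with positive findings of LM on MRI at screening, response categories will be CR", with persisting LM findings as the other category.
- Section 14.2, CSF: "Response will be based on standard cytological analysis if cytology was positive at screening".
- Section 14: "For LM, CR also requires the complete resolution of symptoms and signs attributed to LM".
- Footnote 2 to Table 14-1: "Diagnosis of BM CR or PR, or LM CR, requires that steroids be at or lower than dose of steroids" at Cycle 1 Day 1.

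On eligibility, section 8.2 says "Subjects in Cohort A may have asymptomatic LM detected by MRI", and section 8.6 says the same for Cohort C. LM is therefore optional in those cohorts. In Cohort B it is BM that is optional: "Concomitant brain metastases and brain metastases previously treated with radiation therapy are allowed" (section 8.4).

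**The concern.** Row 5 credits a complete response to a compartment in which no disease is recorded, while every other compartment is unchanged. Under sections 14 and 14.2 a subject who never had LM has no route to an LM CR.

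This matters because the table serves as a derivation rule and the pattern in row 5 is an ordinary one: stable peripheral disease, stable BM and no LM. A programmer who follows the examples literally could record that subject as an LM-only CR instead of stable disease (SD) in the summary response and in best overall response. The subject might then also be counted under duration of response.

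**Working it through.** **The plan's own figure nearby.** Protocol section 16.2 and SAP section 1.2.1 give the chance of at least 3 and at least 2 responders at a 20% rate; the SAP states N = 20.

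- P(at least 3) = 1 − [0.8^20 + 20(0.2)(0.8^19) + 190(0.2^2)(0.8^18)] = 1 − (0.0115 + 0.0576 + 0.1369) = 0.794, against about 80% stated.
- P(at least 2) = 1 − (0.0115 + 0.0576) = 0.931, against over 90% stated.

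Both reproduce. They rest on BM response (Cohorts A and C) or LM symptom improvement (Cohort B), so row 5 does not enter them.

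**The table, row by row.** N = non-CR, non-PD; fn2 = carries footnote 2.

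| Row | Peripheral (measurable / non-measurable) | BM (measurable / non-measurable) | LM | Summary |
|---|---|---|---|---|
| 1 | CR / CR | CR fn2 / CR fn2 | CR fn2 | CR in all three |
| 2 | N / N | PR fn2 / None | N | PR, BM |
| 3 | N / N | CR fn2 / CR fn2 | N | CR, BM |
| 4 | N / N | N / N | CR fn2 | CR, LM |
| 5 | N / N | N / N | None | CR, LM |
| 6 | N / N | CR fn2 / None | CR fn2 | CR, BM and LM |
| 7 | N / N | N / N | N | SD |

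**Row 5 against the text.** An LM CR needs LM shown by MRI or cytology at screening, clearance on each modality that was positive, and resolution of LM symptoms and signs. If *None* means LM absent, the first condition fails and no LM response category applies. This is a clear conflict with separate protocol text.

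**Row 5 against its neighbours.**

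- The summary includes an LM CR in 4 of 7 rows (1, 4, 5, 6). In three of these (1, 4, 6) the LM cell is CR with footnote 2; row 5 is the exception.
- Rows 5 and 7 differ in one input cell, LM. Persisting LM gives SD; *None* gives CR.
- Rows 5 and 4 also differ only in the LM cell, yet share a summary.
- In rows 2 and 6, *None* stands for non-measurable BM beside a response in measurable BM, which fits a component that is absent.

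**Which example fits a stable subject without LM?** *None* appears in the LM column once, in row 5. Row 7 is the only SD example and requires LM to be present. Row 5 is therefore the only match.

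**Which planned outputs are exposed?** SAP Table 1 lists 10 tables, 6 figures and 8 listings, 24 in all. None is titled best overall response, duration of response or duration of stable disease. The outputs for progression-free survival and time to progression are untouched, because CR and SD are both non-progression.

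**The case against.** The strongest reply is that the text governs. The table is headed as examples, the definitions are in sections 14 and 14.2, and an LM response in a subject without LM would be a visible data error. The label is also confined to LM; it is not an overall CR. This lowers the risk, but the protocol explicitly bases three outcomes on these examples, so a wrong example should not be left for an analyst to catch.

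A second reply is that the row may be a typing or layout slip. The text was read from PDF, and the table legend has other slips: BM is expanded as bone metastases and PR as progressive response. Row 5 has all six cells in place, so an extraction fault looks unlikely, but it cannot be excluded.

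A third is that *None* could mean no LM remaining. The protocol never defines the word, and that sense fits the MRI definition of CR. Row 5 would then duplicate row 4, omit the steroid footnote and leave no example for a stable subject without LM. It would still need correcting.

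Three stronger readings are tempting, and the documents do not support them:

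- *The primary response rates are inflated.* The primary objectives are BM response by RECIST 1.1 (A and C) and improvement in LM symptoms and signs (B). In row 5 the BM cells stay non-CR, non-PD. The documents give neither the share of stable subjects nor the share without LM, so any calculated shift would rest on assumptions alone.
- *Such subjects certainly move from duration of stable disease to duration of response.* Appendix A starts duration of response when measurement criteria for CR or PR are met, and makes best response depend on measurement and confirmation. A row 5 subject meets no such criterion. Appendix A is headed for non-CNS response, so it weakens the inference without removing it.
- *Each mismatch with another row is a further contradiction of the protocol.* Only the conflict with sections 14 and 14.2 is a clear conflict with separate text. The comparisons within the table, including the missing footnote mark, are supporting signs.

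**Conclusion.** The point holds as a minor inconsistency in a derivation rule. One of seven examples conflicts with the definition of LM CR and, applied literally, could class a stable subject without LM as an LM-only CR instead of SD in the summary response, best overall response and possibly the durations. The number of subjects cannot be estimated.

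The primary endpoints as defined do not rest on row 5. That is narrower than saying the table has no bearing on them: the steroid condition for a BM CR or PR is stated only in its footnote 2. SAP table 1.1.1 also reports ORR, CR and PR without naming the compartment. The conclusion assumes that it uses BM response in A and C and symptom improvement in B. It further assumes that the row is printed as read here.

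**What to change.** Verify row 5 against the source table, then correct it according to what was meant:

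- LM absent at screening: change the summary to SD.
- LM CR in a subject without BM: set both BM cells to *None* and the LM cell to CR with footnote 2.
- Repeat of row 4: delete it and add an SD example with LM *None*.

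In every case add a footnote that *None* means the compartment was absent at screening and that such a compartment cannot contribute a CR. One sentence in the SAP naming the compartment behind table 1.1.1 would remove the assumption noted in the verdict.

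The cost is one table row and one footnote, plus the optional SAP sentence. Data collection, subjects and the outputs listed in the SAP are unaffected.

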--	---

	symptoms or signs of brain metastases.
Dosage and administration	
Tesevatinib will be administered at the dose of 300 mg once daily. Tesevatinib will be used in dosage strength of 100-mg, and 150-mg tablets. Patient diaries will be utilized to evaluate compliance. One cycle will be defined as 28 days of treatment.
 
Tesevatinib should be taken in the morning (unless there is a subject-specific rationale to take it regularly at a different time of day) and can be administered without regard to food intake.

Duration of treatment/ Discontinuation	
Duration of treatment: Subjects will be treated with study drug until disease progression or unacceptable toxicity occurs. However, subjects with limited peripheral disease progression (oligoprogressive disease) may receive local ablative (radiation therapy or surgery) while study drug is withheld for up to 28 days, and then be continued on tesevatinib.
 
Discontinuation: Subjects who discontinue tesevatinib treatment will be followed for survival.

Concomitant medications	
Concomitant treatment and medication information will be collected from the time the subject signs the informed consent form until 30 days after their last dose of study drug or until the subject starts a new treatment, and is to be reported on the appropriate case report form (eCRF). The generic name of the drug (or trade name for combination drugs) must be specified along with the reason for use, and duration of treatment. Additionally, all diagnostic, therapeutic, or surgical procedures, whether relating to malignancy or not, should be recorded in the eCRF including the date, indication, description of the procedure(s), and any clinical finding. Any medication that is considered necessary for the subject's welfare may be given at the discretion of the investigator. Ancillary treatments will be given as medically indicated. The reason for administration must be recorded on the eCRF. Any changes in documented, permitted concomitant treatment already being taken at the beginning of the clinical study must be recorded in the eCRF, noting the type of medication, the duration, and indication. Concurrent treatment with bisphosphonates or denosumab is allowed, if started prior to the start of tesevatinib administration.

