Prohibited treatments	
 • Other investigational drugs • Concurrent anti-tumor therapies such as chemotherapy, gene therapy, biologics, tyrosine kinases inhibitors, radiation therapy, or other immunotherapy • Medications associated with torsades de pointes or known to moderately or severely prolong the QTc(F) interval, including anti-arrhythmic medications within 2 weeks prior to Day 1 of treatment in the study. • Tesevatinib is largely metabolized by CYP3A4. Therefore, taking any medication known to moderately or severely inhibit the CYP3A4 isozyme or any drugs that are CYP3A4 inducers (including anti-epileptic agents such as phenytoin). A stable regimen (≥ 4 weeks) of antidepressants of the SSRI class is allowed (common SSRIs include escitalopram oxalate, citalopram, fluvoxamine, paroxetine, sertraline, and fluoxetine).

	
 • Steroid medications are allowed • Use of proton pump inhibitors, H2 antagonists, and antacids is allowed, with restrictions • Tesevatinib is a MATE inhibitor. MATE transporter substrates and/or inhibitors should be used with caution

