9 STUDY ASSESSMENTS AND PROCEDURES

Informed consent must be obtained before any study-specific samples are taken or study-specific tests or evaluations are conducted. Screening assessments should be performed within 28 days before the first dose of study drug is administered on Day 1. Study eligibility will be based on satisfying all of the study inclusion and exclusion criteria for each cohort.

Study Day 1 is defined as the date the subject takes the first dose of study drug, with subsequent study days numbered sequentially thereafter.

If significant changes from Cycle 1 Day 1 are noted during the course of the study, additional unscheduled clinic visits may be undertaken by the investigator, or requested by the sponsor, in order to determine both the relevance of the finding(s) and the duration of the event(s).

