‘Cystic lesions’ thought to represent cystic metastases can be considered as measurable lesions, if they meet the definition of measurability described above. However, if non-cystic lesions are present in the same subject, these are preferred for selection as target lesions.

Target lesions: All measurable lesions up to a maximum of 2 lesions per organ and 5 lesions in total, representative of all involved organs, should be identified as **target lesions** and recorded and measured at Screening. Target lesions should be selected on the basis of their size (lesions with the longest diameter), be representative of all involved organs, but in addition should be those that lend themselves to reproducible repeated measurements. It may be the case that, on occasion, the largest lesion does not lend itself to reproducible measurement in which circumstance the next largest lesion which can be measured reproducibly should be selected. A sum of the diameters (longest for non-nodal lesions, short axis for nodal lesions) for all target lesions will be calculated and reported as the Screening sum diameters. If lymph nodes are to be included in the sum, then only the short axis is added into the sum. The Screening sum diameters will be used as reference to further characterize any objective tumor regression in the measurable dimension of the disease.

Non-target lesions: All other lesions (or sites of disease) including any measurable lesions over and above the 5 target lesions should be identified as **non-target lesions** and should also be recorded at Screening. Measurements of these lesions are not required, but the presence, absence, or in rare cases unequivocal progression of each should be noted throughout follow-up.

Methods for Evaluation of Measurable Disease

All measurements should be taken and recorded in metric notation using a ruler or calipers. All Screening evaluations should be performed as closely as possible to the beginning of treatment and never more than 4 weeks before the beginning of the treatment.

The same method of assessment and the same technique should be used to characterize each identified and reported lesion at Screening and during follow-up. Imaging-based evaluation is preferred to evaluation by clinical examination unless the lesion(s) being followed cannot be imaged but are assessable by clinical exam.

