Clinical lesions: Clinical lesions will only be considered measurable when they are superficial (e.g. skin nodules and palpable lymph nodes) and ≥ 10 mm diameter as assessed using calipers (e.g. skin nodules). In the case of skin lesions, documentation by color photography, including a ruler to estimate the size of the lesion, is recommended.

Chest X-ray: Lesions on chest X-ray are not acceptable as measurable lesions in this study.

Conventional CT and MRI: This guideline has defined measurability of lesions on CT scan based on the assumption that CT slice thickness is 5 mm or less. If CT scans have slice thickness greater than 5 mm, the minimum size for a measurable lesion should be twice the slice thickness. MRI in this study is required for evaluation for brain metastases.

FDG-PET-CT: Not acceptable for this study.

Ultrasound: Not acceptable for this study.

Endoscopy, Laparoscopy: Not acceptable for this study.

FDG-PET: Not acceptable for this study.

Response Criteria

Evaluation of Target Lesions

- Complete Response (CR):** Disappearance of all target lesions. Any pathological lymph nodes (whether target or non-target) must have reduction in short axis to < 10 mm.
- Partial Response (PR):** At least a 30% decrease in the sum of the diameters of target lesions, taking as reference the Screening sum diameters.
- Progressive Disease (PD):** At least a 20% increase in the sum of the diameters of target lesions, taking as reference the smallest sum on study (this includes the Screening sum if that is the smallest on study). In addition to the relative increase of 20%, the sum must also demonstrate an absolute increase of at least 5 mm. (Note: the appearance of 1 or more new lesions is also considered progression).
- Stable Disease (SD):** Neither sufficient shrinkage to qualify for PR nor sufficient increase to qualify for PD, taking as reference the smallest sum

diameters while on study.

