# 1.3 Efficacy Assessments

## 1.3.1 Efficacy Endpoints

## 1.3.1.1 Primary endpoints

Cohorts A and C: efficacy (changes in BM size) will be evaluated by RECIST 1.1 criteria separately for non-CNS tumor lesions and for BMs at screening, at Cycle 2 Day 1 (for BM), at Cycle 3 Day 1, and then every 2 cycles (approximately 8 weeks) thereafter until disease progression.

For Cohort B: symptoms and signs attributed to leptomeningeal disease will be evaluated at screening, Cycle 1 Day 1, at Cycle 1 Day 14, at Cycle 2 Day 1, at Cycle 3, and then every 2 cycles (approximately 8 weeks) thereafter until disease progression National Cancer Institute CTCAE (NCI CTCAE; Version 5). Symptom improvement is defined as a decrease in 1 grade in at least one CTCAE v4.03 symptom or sign attributed to LM without worsening of other symptoms or signs that are attributed to LM. Symptom progression is defined as an increase of 1 grade in at least one CTCAE v4.03 symptom or the appearance of new symptoms or signs of LM.

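### The steroid condition on brain-metastasis response refers to the Cycle 1 Day 1 dose, but shrinkage is measured from the Screening MRI, so steroid changes between the two dates are judged against the wrong reference

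*Protocol*

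**What the plan says.** Two reference dates govern BM response, the primary endpoint of Cohorts A and C.

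- **Steroids.** Protocol Section 14, Table 14-1 footnote 2: a BM CR or PR "requires that steroids be at or lower than dose of steroids at Cycle 1 Day 1 (if subject is receiving steroids").
- **Size.** Protocol Appendix A defines PR as "At least a 30% decrease in the sum of the diameters of target lesions, taking as reference the Screening sum diameters".
- **Age of the size reference.** Appendix A asks for Screening evaluations as near the start of treatment as possible and "never more than 4 weeks before the beginning of the treatment". Section 9 agrees: "Screening assessments should be performed within 28 days before the first dose of study drug is administered on Day 1".
- **Scan schedule.** Section 14: "Radiological disease assessments by brain MRI will be performed at screening, at C2D1, at C3D1, and then every two cycles until disease progression". Table 4-1 shows no tumour assessment on Cycle 1 Day 1.
- **Steroid use.** The Synopsis entry on prohibited treatments says "Steroid medications are allowed", and Section 12 repeats it. The BM-cohort criteria (Sections 8.2, 8.3, 8.6 and 8.7) set no stable-dose period for steroids, although they set one of at least 4 weeks for SSRIs.
- **SAP.** Section 1.3.1.1: "Cohorts A and C: efficacy (changes in BM size) will be evaluated by RECIST 1.1 criteria". The SAP does not mention steroids.

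**The concern.** Footnote 2 exists because steroids can make brain metastases look smaller. To do that job it should compare the steroid dose at the response scan with the dose at the scan that supplies the size reference. It compares it with the dose on a later day, when no scan is taken. Whatever happens to the steroid dose between the Screening MRI and Day 1 is therefore invisible to the condition, although it falls inside the interval over which shrinkage is measured.

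The study is open-label and uncontrolled (Protocol Section 7.3), so no comparison arm absorbs a steroid effect. Steroid use is foreseeable: Cohorts A and C admit minimally symptomatic BM, and Cohort C states that prior systemic steroids do not count as systemic NSCLC treatment.

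**Working it through.** **1. The plan's own figures.** Protocol Section 16.2 and SAP 1.2.1 use n = 20 and a response rate of 0.20.

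- P(X ≥ 3) = 1 − [0.8^20 + 20(0.2)(0.8^19) + 190(0.2²)(0.8^18)] = 1 − [0.0115 + 0.0576 + 0.1369] = 0.794. The plan says about 80%.
- P(X ≥ 2) = 1 − [0.0115 + 0.0576] = 0.931. The plan says over 90%.

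Both reproduce. The point disputes neither.

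**2. The interval.** The Screening MRI can be up to 28 days before first dose. Cycle 2 Day 1, the first follow-up MRI, comes one 28-day cycle after Day 1. The first size comparison can therefore span 28 + 28 = 56 days before visit windows, and footnote 2 ignores steroid changes in the first 28.

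**3. The rule applied.** Let d0 be the steroid dose at the Screening MRI, d1 the dose at Cycle 1 Day 1 and d2 the dose at a later scan. Footnote 2 requires d2 ≤ d1. A like-for-like comparison with the size reference requires d2 ≤ d0.

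| Steroid change before Day 1 | Dose at later scan | Footnote 2 (d2 ≤ d1) | Like for like (d2 ≤ d0) |
|---|---|---|---|
| None (d1 = d0) | d2 = d0 | passes | passes |
| Started or raised (d1 > d0) | d2 = d1 | passes | fails |
| Tapered (d1 < d0) | d1 < d2 ≤ d0 | fails | passes |

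The second row can credit steroid-related shrinkage to the drug. The third can deny a response although the dose does not exceed that at baseline.

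**4. Whether anything else closes the gap.**

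- Confirmation at 4 weeks or more (Appendix A) does not, because the raised dose stays permitted at the confirming scan.
- Central review (Section 14) does not, because it reads the same scans against the same baseline.
- The exclusion of other concurrent BM therapy cannot be read as barring steroids, since Section 12 allows them and footnote 2 presupposes them.
- The SAP adds no steroid rule.

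**5. Size.** One subject in 20 is 1/20 = 5 percentage points. With exact (Clopper-Pearson) 95% intervals, 2/20 is 10% (1.2% to 31.7%) and 3/20 is 15% (3.2% to 37.9%).

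The documents give no frequency. As an illustration, let q be an assumed chance that a true non-responder is counted as a responder by this route, with true rate p. The apparent rate is p + (1 − p)q.

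| p | q = 0 | q = 5% | q = 10% |
|---|---|---|---|
| 10% | 10% | 14.5% | 19% |
| 20% | 20% | 24% | 28% |

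For example, 0.10 + 0.90 × 0.05 = 0.145. These q values are not estimates. The table covers only the start-or-raise route; tapers work the other way.

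**The case against.** Several arguments against the point carry weight.

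- **Direction.** A reader might infer that the bias can only inflate response. It cannot be put that strongly: a pre-Day 1 taper makes the rule stricter, and tumour growth between the Screening MRI and first dose also counts against response.
- **Frequency.** A reader might infer that steroid starts in this window are common. The documents do not say so. Twenty-eight days is a ceiling, Appendix A asks for scans as near to treatment as possible, and subjects without prior brain radiotherapy must be asymptomatic or minimally symptomatic. Nor do the documents show that steroids alone produce a 30% fall that survives confirmation.
- **Three responders as a threshold.** Moving from 2 to 3 responders crosses nothing. The count appears only in the sample-size statement, SAP Section 2 rules out formal hypothesis testing, and the two intervals above largely overlap.
- **Dose not collected.** The Synopsis says the drug name "must be specified along with the reason for use, and duration of treatment", without listing dose. That does not show that dose is missing: Section 12 requires medication details on the eCRF, and the eCRF is not among the documents.
- **SAP silence.** Naming RECIST 1.1 without the steroid condition does not revoke footnote 2. It leaves the programming of the response tables open.
- **Terminology.** Appendix A is headed for non-CNS response, and Protocol Section 16.3.6 describes change from Cycle 1 Day 1 tumour measurements. But Sections 14 and 14.1 apply RECIST 1.1 to BM, Appendix A covers brain MRI, and no Day 1 scan exists. In practice the size reference is the Screening scan.

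These objections limit direction, frequency and consequence. None removes the date mismatch.

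**Conclusion.** The mismatch stands on the protocol's text. Followed exactly, footnote 2 lets a steroid start or increase between the Screening MRI and Day 1 contribute to a counted BM CR or PR. It can also withhold a response after a taper in that window. Each misclassified subject moves a 20-subject cohort's rate by 5 percentage points. The number of such subjects, and the net direction, cannot be derived from the documents.

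The conclusion rests on two readings: that the Screening sum is the size reference for BM, and that steroids can affect apparent lesion size, which footnote 2 itself presupposes. It does not support a claim that the primary result will be materially inflated, or that a go/no-go decision is at risk. It is a should-fix item: a small flaw in the only steroid safeguard on the primary endpoint of two cohorts.

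**What to change.** 1. **Protocol, Table 14-1 footnote 2.** For BM CR and PR, make the reference the systemic corticosteroid dose at the time of the baseline (Screening) brain MRI, so that steroid dose and lesion size share one date.
2. **SAP 1.3.1.1 and Tables T 1.1.1 and T 1.1.2.** State that this condition applies to BM CR and PR in Cohorts A and C.
3. **Sensitivity analysis.** Repeat the response rate counting responders with a steroid start or increase between the baseline MRI and Cycle 1 Day 1 as non-responders. Concomitant medication is already recorded from consent (Protocol Section 9.1.16) and listed in SAP L 3.1.1. Confirm that the eCRF captures steroid dose with dates.
4. **Wording.** Reconcile the references to Cycle 1 Day 1 tumour measurements or lesions (Synopsis statistical methods, Section 16.3.6, Appendix A) with the Screening reference.

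These changes affect how response is classified, not how subjects are treated, and need no extra visit, scan or subject. The cost is that the reported rate may be lower: a true responder whose steroids were raised in the window and not reduced would not count. A reference set at the lower of the two doses would go further than aligning the dates and is not needed.
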